5.3.8.3. Pharmacokinetic/ Pharmacodynamic Analyses

The plasma concentration versus time data together with information on dosing and patient characteristics will be pooled and analyzed using a population PK analysis approach. Nonlinear mixed effect modeling (NONMEM) will be used for the estimation of the population PK parameters of LY2157299.

The PK parameter of interest will be evaluated with dose concentration and fix effects (such as weight or age) in the model. Interindividual variation and residual variation will also be reported.

The plasma concentration will be summarized descriptively and presented graphically in JBAK study report.

In addition, data from patients in this study may be combined with data from JBAH study, for PK population analysis.

In Part C, Cycle 1 assesment of possible sorafenib exposure change during monotherapy and combination will be made.

Exploratory PK/PD analyses will be conducted to identify the exposure-response (biomarker) relationship in this study. The PK and PK/PD analyses may be reported as separate stand-alone reports for this study. Additional analyses on exposure-response using TTP and/ or other clinical endpoints may be explored if data warrant.

Lilly Pharmacokineticist will be responsible for this analysis. Details on the analysis can be found in the Pharmacokinetic plan.

5.3.8.4. Health Outcome Analyses

The following will be carried out for each part separately.

Questionnaire compliance rates will be ascertained at each assessment: baseline (prestudy), day 1 of every cycle starting from cycle 2, and discontinuation (Visit 801).

For those patients who completed at least one questionnaire, summary descriptive statistics of FACT-Hep subscales scores (PWB, SWB, EWB, FWB, HCS), NCCN-FACT subscales scores based on FACT-Hep (NFHSI-DRS-14, NFHSI-FWB-3, NFHSI-TSE-1), total scores (FACT-G, FACT-Hep, TOI, NFHSI-18) and individual symptoms from the HCS subscales will be provided at each time point by dosing cohort and pooled. This summary will include number of patients, number of patients with completed questionnaire, mean, standard deviation, median, minimum, and maximum scores.

J.L Steel (2005) has estimated minimally important differences (MIDs) in FACT-Hep based on 158 patients diagnosed with hepatobiliary carcinoma (85% of patients with HCC) to help interpret individual and group differences on HRQoL measures. The MIDs are given as follows: (1) FACT-Hep subscales: 2 – 3; (2) FACT-G: 6 – 7; (3) FACT-Hep: 8 – 9; (4) HCS: 5 – 6; (5) TOI: 7 – 8; and (6) FHSI-8: 2 – 3. These MIDs will be used to assess and interpret change from baseline scores.

For those patients who completed a baseline and one post-baseline questionnaire, change from baseline on subscale and total scores will be assessed. Repeated measures ANOVA will be performed on each cohort to test changes over time from baseline (pre-study) to patient discontinuation at visit 801. P-values indicating significant differences will be provided. Same analysis will be performed on pooled data from both cohorts. Waterfall plots of change from baseline of individual patients will be provided. Plots of mean subscale scores, total scores, TOI and NFHSI-18 over time will be provided.

Time to worsening of symptoms, using the MIDs as a reference, will also be evaluated for PWB, FWB, HCS, TOI and NFHSI-18. For example, a decrement in score of 2 or 3 in PWB would consider a worsening of symptoms. Data from each dosing cohort and pooled will be analyzed

using Kaplan-Meier plots with censoring at the last assessment for patients with no worsening. Median time to worsening with 95% confidence interval will be provided.

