5.1.5.2. JBAK: Brief Summary of Results to Date

At the time of Amendment (e), Part A and Part B of the study have completed. A total of 149 patients were enrolled (109 in Part A and 40 in Part B). Eighty-five percent of patients were male and the median age was 65 years. Fifty-six percent of patients had an ECOG performance status (PS) of 0 and 44% had a PS of 1. Eighty-six percent of patients had a Child-Pugh Class A score and 14% had a Class B score. Etiology of disease was as follows: hepatitis C 24%, hepatitis B 20%, alcohol 20%; multiple 9.4%. Overall, 83% of patients had received prior sorafenib. Eleven patients discontinued treatment due to AEs: 8 were considered related to study treatment. Grade 3/4 AEs possibly related to treatment were observed in 26 (17%) patients. Of these AEs, neutrophil count decrease was observed in 4 patients. Anemia, hypoalbuminemia, decreased bilirubin, fatigue and embolism were observed in 2 patients each. All other AEs occurred in just 1 patient. Median TTP was 11.9 weeks (95% CI: 6.3, 12.6) in Part A and 18.0 weeks (95% CI: 10.0, 24.0) in Part B. Median OS was 31.4 weeks (95% CI: 22.9, 40.6) in Part A and 73.0 weeks (95% CI: 45.4, 104.7) in Part B. The median OS for the overall population was estimated as 40.4 weeks (95% CI: 31.1, 52.4) (Giannelli et al. 2016).

Enrollment into Part C has completed and maturation of the data is awaited. Enrollment is ongoing in Part D of the study.

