12.2.11. Health Outcome/Quality of Life Analyses

The following will be carried out for each part separately.

Questionnaire compliance rates will be ascertained at each measurement time point until the end of study therapy including at discontinuation (Visit 801).

Summary descriptive statistics will be provided for the PRO data (FACT-Hep) at each assessment. This summary will include mean, standard deviation, median, minimum, maximum, and change from baseline. Scores will be evaluated both in aggregate (that is, median values for each study arm at a given time point) and individually, in which each patient's score on study is evaluated relative to his/her baseline score. Time to worsening of symptoms will also be evaluated, and longitudinal analyses, such as repeated measures, will be performed. FACT subscales, total score, trial-outcome index, and symptoms (FHSI-8) will be assessed per the established scoring algorithm.

Other exploratory longitudinal analyses may be performed.

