5.3.4. Handling of Missing Data

For time-to-event endpoints, the method for handling missing data will be censoring. Patients that withdrew from the study without response will be censored for response at the date of the last tumor assessment.

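### FACT-Hep change is tested by repeated measures ANOVA to Visit 801 with no rule for missing questionnaires and no common visit set; a classical fit would drop many patients and can understate deterioration

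*SAP*

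**What the plan says.** SAP 5.3.8.4 (Health Outcome Analyses) plans that "Repeated measures ANOVA will be performed on each cohort to test changes over time", with the pre-study form as the start and V801 as the end. P-values are to be given, and the analysis is repeated on the pooled cohorts. The population is set one sentence earlier: "For those patients who completed a baseline and one post-baseline questionnaire, change from baseline on subscale and total scores will be assessed". Forms are due before treatment, on Day 1 of each cycle from Cycle 2, and at V801.

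Protocol 12.2.11 is looser: "longitudinal analyses, such as repeated measures, will be performed". SAP 5.3.4 (Handling of Missing Data) says "For time-to-event endpoints, the method for handling missing data will be censoring" and adds a sentence on tumour response. It is silent on longitudinal scores. SAP 5.1.2 prorates missing items within a form but does not deal with missing forms.

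The same section also plans compliance rates, summaries at each visit, waterfall plots and a time-to-worsening analysis "using Kaplan-Meier plots with censoring at the last assessment for patients with no worsening".

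**The concern.** Classical repeated measures ANOVA needs the same visits from every patient and deletes anyone with a gap. This study cannot supply that. Treatment has no fixed end (Protocol 7.1), so the number of forms differs by patient. V801 follows discontinuation (Protocol 10), so it may come after one cycle or after ten.

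Leaving is also plausibly linked to the score. From Amendment (b), asymptomatic patients may continue past radiological progression and then stop for symptomatic deterioration (Protocol 10.1; SAP 5.1.1). Symptoms are part of what FACT-Hep measures.

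At stake is a secondary objective. A real decline in quality of life could look smaller than it is because the patients analysed are those who stayed.

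**Working it through.** **1. Can the analysis be run as written?** Baseline to V801 is not a common set of time points:
- A patient still on treatment has no V801 form.
- A patient who stopped early has V801 but no later cycles.
- Only someone who passed the last modelled cycle and then stopped has every level, and the last modelled cycle is not stated.

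For biomarkers, SAP 5.3.8.2 names a mixed-effects model with patient as a random effect and a covariance structure chosen from the data. The FACT-Hep text names neither.

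**2. How many patients would a complete-visit analysis lose?** Neither document gives time on treatment, so TTP serves as a proxy. Protocol 5.1.5.2 reports "Median TTP was 11.9 weeks (95% CI: 6.3, 12.6) in Part A", and 18.0 weeks (95% CI 10.0 to 24.0) in Part B, with 109 and 40 patients enrolled. Assume exponential retention, S(t) = 0.5^(t/median).

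Check on the formula: Protocol 12.1 gives 63% and 50% progression-free at 3 months for medians of 4.5 and 3 months. 0.5^(3/4.5) = 0.630 and 0.5^(3/3) = 0.500, so both agree.

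Cycle 6 Day 1 is week 20 (5 cycles of 4 weeks).

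| | Retained at week 20 | Over the CI of the median | Lost |
|---|---|---|---|
| Part A | 0.5^(20/11.9) = 0.312, about 34 of 109 | 11% to 33% | 69% |
| Part B | 0.5^(20/18.0) = 0.463, about 18.5 of 40 | 25% to 56% | 54% |

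Pooled: (34.0 + 18.5)/149 = 35% retained. No median TTP is given for Parts C, D or E.

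**3. What could that do to the estimate?** The plan gives no expected FACT-Hep change, variance or dropout model, so there is no figure to reproduce and every input here is an assumption: 4,000 simulated patients; baseline mean 130 (SD 18); slope -2 points per cycle (SD 2.5); residual SD 7; average dropout per cycle 1 - 0.5^(4/11.9) = 0.21. The expected change at Cycle 6 Day 1 is 5 × (-2) = -10. V801 scores are left out of the first two estimates. The mixed model has categorical visits and unstructured covariance.

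| Dropout depends on | True change in the sample | Complete visits only | Mixed model, all scores | Baseline to last score, V801 included |
|---|---|---|---|---|
| Nothing | -10.1 | -9.9 | -10.1 | -6.7 |
| Last observed score | -10.3 | -2.0 | -10.2 | -6.1 |
| Patient's own unobserved slope | -10.2 | -1.9 | -4.0 | -4.7 |

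The third row is numerically delicate. A random-slope version of the mixed model gives -4.3 once converged, and -3.7 if the optimiser stops early. All of these remain far from -10.

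A second set of assumptions (72 patients, slope -0.6 per week, hence -12 at week 20; intercept SD 12, slope SD 0.8, residual SD 6) gives complete-case estimates of -8.3 and -5.6 under a moderate and a stronger link of dropout to the last score. The likelihood estimates are -12.1 and -12.0. With random dropout both methods are unbiased, but the SD of the estimate is 3.6 against 2.9.

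The complete-case shortfall is therefore close to nil under random dropout, 3.7 or 6.4 points in the second set, and 10.3 - 2.0 = 8.3 points in the first. SAP 5.3.8.4 cites 8 to 9 points as the important difference for the FACT-Hep total.

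**4. What does treating V801 as one time point do?** The last column takes the discontinuation score as the score due at the next cycle. Even when dropout is random, the mean change to the last score is -6.7, not -10.1, because many last scores come earlier. It averages over different durations and is not the change at any stated time.

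**The case against.** The strongest reply is that the SAP never restricts the test to complete visits. Its entry set is a baseline form plus one later form, and the protocol names repeated measures only as an example. A reader might infer listwise deletion from the method's name, but the text is equally open to a model on all available data. That stands: the fault is that the choice is left open, and the deletion is a consequence only if the classical form is used.

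A reader might also infer that most patients are off treatment by Cycle 6. The documents do not say so. Treatment past progression is allowed, and Protocol 5.1.7 notes patients staying beyond 4 months, so TTP may understate time on treatment. Patients also stop for reasons other than progression. For Part B the proxy interval of 25% to 56% retained spans one half.

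Nor do the documents support saying that the analysis will report stable quality of life. Direction and size depend on why patients leave. Even the complete-case figures of -8.3 and -5.6 are declines, and -8.3 lies within the important-difference range. The complete-case simulations omit V801, where patients who stop are due to give a score, so they do not reproduce the planned analysis.

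The other planned outputs need no complete visits, but they do not close the gap. Visit-level means describe whoever remains. Time to worsening leaves out the FACT-Hep and FACT-G totals, and its censoring at last assessment can itself be informative.

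**Conclusion.** The concern holds as a gap in specification with a plausible bias, not as a demonstrated one. Three things follow from the text alone: repeated measures ANOVA is the named test, no rule covers missing scheduled FACT-Hep forms, and V801 has no defined place on the time axis.

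The losses of about 69% (Part A) and 54% (Part B) rest on TTP as a proxy, exponential retention and a complete-visit fit through Cycle 6. Understatement requires dropout to follow worsening, which the stopping rules make plausible; its size cannot be fixed from the documents. A mixed model removes the bias when dropout depends on observed scores. When dropout follows an unobserved trend, it only reduces it.

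The endpoint is secondary and the test is within cohort, so the primary TTP objective is untouched. The change should be made, but nothing in the primary analysis depends on it.

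**What to change.** Replace the ANOVA in SAP 5.3.8.4 with a likelihood-based mixed model for repeated measures that:
- uses every available score from patients with a baseline and at least one later form;
- treats visit as categorical over a stated set of cycles, with baseline score as covariate;
- uses an unstructured covariance, with a named simpler structure if the model fails to converge in small cohorts (Part A Cohort 1 closed at 37 patients).

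State that V801 enters at its actual time since first dose, or is analysed separately as change at discontinuation. Add a sensitivity analysis for informative dropout, such as a pattern-mixture or shared-parameter model, and show the number of forms at each visit beside the estimates.

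The cost is SAP wording and a little more analysis. Protocol 12.2.8 already calls for an amended SAP before Part E dosing, which could carry the text. Parts A and B had completed by Amendment (e), so they would need re-analysis. No new data are required.

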5.3.9. Safety Analyses

5.3.9.1. Study Drug Exposure

The number of cycles completed per patient and dose intensity will be summarized using descriptive statistics (mean, median, minimum, and maximum).

Dose intensity for LY2157299 is derived according to the following formula:

- Planned cumulative dose (mg):

$$PLC_i = \text{number of cycles} * \text{assigned dose per day} * 14$$

where 14 is the planned number of dosing days per cycle.

- Prescribed cumulative dose (mg):

PRC_i = sum of prescribed dose multiplied by the number of dosing days in that cycle over all cycles.

The actual dosing is collected on days 1, 12, 13, and 14 of cycle 1 and day 1 of cycle 2, which aligns with the PK sampling day. Any dose modifications collected during the treatment period will be considered in the calculation of prescribed cumulative dose. Additional and/or detailed considerations for deriving of prescribed cumulative dose will be included in the TFL requirements. For interim data cut, the number of cycles up to the last completed cycle for patients in active treatment will be considered for this calculation; for patients that has discontinued from treatment, the number of cycles up to the last cycle will be considered.

- Dose intensity in percent:

$$PDC_i = (PRC_i / PLC_i) * 100\%$$

For each patient, dose intensity for LY2157299 will be listed based on cumulative doses received during study. Note prescribed dose is the same assigned dose if there is no dose modification. Listings of dose assignment and dose information on LY2157299 will also be provided.

Cycle delays, dose reductions, and dose omissions of LY2157299, including reasons, will also be listed. If the reason for dose modification is due to AE, the associated AE will be provided. The number and percentage of patients with any dose modifications will be summarized for the entire treatment period as well as for each cycle.

5.3.9.2. Adverse Events

The adverse events will be reported in CTCAE terms using CTCAE Version 4.0x. Any listings or summaries using MedDRA will use preferred terms in the most current version of MedDRA at the time of reporting. The version of MedDRA used in any reports will be documented.

Treatment-emergent adverse events (TEAEs) are defined as follows:

- Any AE, regardless of causation, that were not present prior to first dose and emerges on or after the day of the first dose of study treatment
- Or any PEC (emerged prior to informed consent) or any AE (emerged after signed informed consent) that were still present prior to first dose but has increased in severity (CTC grade) following the start of treatment, regardless of causation.

A listing of all adverse events by patient, including pre-existing conditions, will be presented. This listing will include patient number, adverse event (actual term, CTCAE term, and preferred term), event start and end dates, CTCAE grade, relationship to study drug/procedure, seriousness, and outcome. A listing of SAE will be produced using the same format.

Adverse events will be summarized by frequency counts and percentages as follows:

- Patients with at least one AE
- Patients with at least one TEAE
- Patients with at least one grade 3 or 4 AE
- Patients with at least one SAE
- Patients who discontinued due to AE
- Patients who discontinued due to SAE
- Patients who died on therapy
- Patients who died within 30 days of last dose of study drug

For each category above, frequency counts and percentages will also be provided for patients who had events possibly related to study drug.

Adverse events in CTCAE terms will be also be summarized by CTCAE grade within the SOC. This summary will be provided for all adverse events with CTCAE grade, regardless of causation, and repeated for possibly drug related AE with CTCAE grade.

TEAEs will be summarized by CTCAE term in decreasing frequency within the SOC, regardless of causation, and repeated for TEAEs that are deemed by investigator to be possibly study drug related. Serious adverse events will summarized in the same format.

A listing of patient discontinuation due to AE or death will also be provided.

Chi-squared test may also be performed to compare AE incidences between the 2 doses and study parts adjusting as necessary for baseline AFP levels or other important variables. Any significant differences (p-value <0.05 or p-value < 0.01) will be indicated in the summaries.

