10.2.1. Adverse Events

Lilly has standards for reporting AEs that are to be followed regardless of applicable regulatory requirements that may be less stringent.

Lack of drug effect is not an AE in clinical trials because the purpose of the clinical trial is to establish drug effect.

Cases of pregnancy that occur during maternal or paternal exposures to study drug or drug delivery system should be reported. Data on fetal outcome and breast feeding are collected for regulatory reporting and drug safety evaluation.

Study-site personnel will record the occurrence and nature of each patient's preexisting conditions, including clinically significant signs and symptoms of the disease under treatment in the study.

After the informed consent form (ICF) is signed, site personnel will record in the electronic case report form (eCRF) any change in the condition(s) and the occurrence and nature of any AEs. All AEs related to protocol procedures are reported to Lilly or designee via eCRF.

In addition, all AEs occurring after the patient receives the first dose of study drug must be reported to Lilly or its designee via eCRF.

Any clinically significant findings from ECGs, labs, vital-sign measurements, other procedures, and so on that result in a diagnosis should be reported to Lilly or its designee via eCRF.

Investigators will be instructed to report to Lilly or its designee their assessment of the potential relatedness of each AE to protocol procedure, studied disease state, study drug, and/or drug delivery system via eCRF.

If a patient's dosage is reduced or treatment is discontinued as a result of an AE, study-site personnel must clearly report to Lilly or its designee via eCRF the circumstances and data leading to any such dosage reduction or discontinuation of treatment.

Events leading to the clinical outcome of death due to progressive disease will be included as part of the safety and efficacy analyses for this study and will not be reported to Lilly or its designee as AEs via eCRF, unless the investigator believes the event may have been caused by the study drug or drug delivery system.

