12.2.12. Safety Analyses

Adverse event (AE) terms and severity grades will be assigned by the investigator using CTCAE v4.0. AE terms will also be derived from verbatims using the Medical Dictionary of Regulatory Activities.

All patients who received LY2157299 will be evaluated for safety. Safety analyses will include, but are not limited to, the following:

- all reported AEs, including seriousness, severity, and possible relationship to study drug, using CTCAE terminology and grades
- TEAEs, including seriousness, severity, and possible relationship to study drug, using CTCAE terminology and grades
- dose adjustments for any study therapy

- physical exam and other safety observations, including those specifically targeting monitoring for cardiac safety
- laboratory measures

Safety analysis may also estimate the difference in the incidence of AEs between the 2 doses and study parts, adjusting as necessary for baseline AFP levels or other important covariates.

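### SAP 5.3.9.2 gives no severity summary for treatment-emergent events, and its severe-event row is built on loosely defined AEs and names only Grades 3 and 4

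*SAP*

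**What the plan says.** Protocol 12.2.12 lists, as one of the safety analyses, "TEAEs, including seriousness, severity, and possible relationship to study drug, using CTCAE terminology and grades". A separate item in the same list asks for the same attributes for all reported AEs.

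SAP 5.3.9.2 plans three outputs that bear on severity:

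- An overview row: "Patients with at least one grade 3 or 4 AE". It is repeated for events possibly related to study drug.
- A table of AEs "summarized by CTCAE grade within the SOC". Its scope is: "This summary will be provided for all adverse events with CTCAE grade, regardless of causation". It is repeated for possibly related AEs.
- A TEAE table: "TEAEs will be summarized by CTCAE term in decreasing frequency within the SOC, regardless of causation". It is repeated for possibly related TEAEs and carries no grade.

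The same section defines a TEAE in two limbs. The first is an event that is new on or after first dose. The second concerns events already there at baseline whose grade rises once dosing begins, and it names two kinds: "any PEC (emerged prior to informed consent) or any AE (emerged after signed informed consent". So a pre-existing condition (PEC) that worsens on drug is a TEAE. The AE listing in 5.3.9.2 includes PECs, and SAP 5.3.6.2 has them graded by CTCAE and placed in that listing.

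**The concern.** The protocol asks for severity on two bases, all AEs and TEAEs, and the SAP delivers it on the first only. The TEAE definition is the one that isolates what emerged or worsened on treatment, and it is the one left without grades.

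The AE basis is not a clean substitute, because the SAP does not say whether PECs belong to it or at which grade they would enter. Two programmers could follow the text and produce different severe-event rates.

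Safety and dose recommendation are secondary objectives (SAP 4.2). A related Grade 3/4 rate is already the summary toxicity figure for Parts A and B in Protocol 5.1.5.2, and SAP 5.3.9.2 allows AE incidences to be tested between doses and Parts. Entry criterion 7 (Protocol 8.1) admits platelets down to 50 x 10^9/L, hemoglobin down to 8 g/dL and ALT/AST up to 5 x ULN. Worsening from an abnormal baseline is therefore a realistic route to a severe event in this population.

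**Working it through.** The plan states no figure for this point, so the check is mainly a comparison of texts.

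**Step 1: protocol against SAP.** Protocol 12.2.12 requires grades for all AEs and for TEAEs. SAP 5.3.9.2 has a grade table and a Grade 3/4 row for AEs. For TEAEs it has a count of patients with at least one, and a table by term. It plans no TEAE summary by grade and no severe-TEAE count.

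**Step 2: what counts as an AE in the severity outputs.** Two readings are open.

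- *Reading 1, PECs are not AEs.* The TEAE definition separates a PEC, which began before consent, from an AE, which began after it.
- *Reading 2, PECs are AEs.* The listing sentence in SAP 5.3.9.2 includes PECs among adverse events, SAP 5.3.6.2 grades them there, and Protocol 10.2.1 has sites record changes in pre-existing conditions alongside AEs.

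| Patient's only relevant event | Grade 3/4 AE row, reading 1 | Grade 3/4 AE row, reading 2 | TEAE by definition? |
|---|---|---|---|
| PEC, Grade 2 before dosing, Grade 3 on drug | not counted | counted, if the worsened grade is used | yes |
| PEC, Grade 3 before dosing, unchanged | not counted | counted | no |
| New Grade 3 event after first dose | counted | counted | yes |
| New event, Grade 5 only | not counted | not counted | yes |

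Reading 1 misses the first patient. Reading 2 wrongly includes the second. Neither matches the last column, so the error can go in either direction.

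**Step 3: Grade 5.** The overview row names Grades 3 and 4, so the fourth patient is outside it on both readings. Under Protocol 10.2.1, events leading to death from progression "will not be reported to Lilly or its designee as AEs via eCRF, unless the investigator believes the event may have been caused" by study drug or the delivery system. The Grade 5 AEs on file are therefore a selected group with a direct bearing on safety.

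**Step 4: scale.** Inputs from Protocol 5.1.5.2 are 149 patients in Parts A and B (109 + 40), of whom 26 had possibly related Grade 3/4 AEs.

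- Reported rate: 26/149 = 17.4%, which agrees with the 17% given.
- Effect of one misclassified patient: 1/149 = 0.67 percentage points.

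The documents give neither the number of worsened or stable PECs nor the number of patients whose only severe event was Grade 5. The total effect cannot be computed.

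**The case against.** The best defence is that little is lost. Every AE is listed with its grade, dates, relatedness and seriousness. A worsened PEC is in the TEAE counts in any case, only without its grade. Hematology and chemistry are summarised by CTCAE grade under SAP 5.3.9.4, which covers the platelet, hemoglobin and transaminase examples. Dose escalation in Parts C and D rests on dose-limiting toxicities, not on these tables. On reading 2, the possibly related version would drop most stable baseline conditions, since investigators would rarely attribute an unchanged condition to the drug. All of this stands and keeps the point modest. It does not supply the TEAE severity summary that the protocol asks for, and the laboratory tables carry no relatedness and do not cover non-laboratory events.

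A reader might also infer three stronger claims that the documents do not support.

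- *Severity tabulation stops at Grade 4 and fatal AEs vanish.* Only the one overview row is so limited. The grade-by-SOC table has no cap. Fatal AEs also reach the SAE row (the SAE definition in Protocol 10.2.1.1 includes death). Deaths on therapy or within 30 days of last dose have their own rows, and SAP 5.3.9.5 lists all deaths with cause.
- *Worsened PECs are lost from the severity tables.* That follows from reading 1 only, and the listing text and SAP 5.3.6.2 favour reading 2.
- *The 17% can be scaled down by an assumed share of worsened PECs.* No share is given, and the 26 patients are an already reported count whose counting rule is not stated. If that rule had left patients out, 26 would be the reduced figure and the full count would be higher.

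**Conclusion.** The point holds as a gap between protocol and SAP. Protocol 12.2.12 calls for TEAE severity by CTCAE grade and SAP 5.3.9.2 does not provide it. The severity outputs it does provide are not tied to emergence or worsening on treatment, so the severe-event rate may be under- or over-counted, depending on a reading that the SAP leaves open. The overview row separately omits a patient whose only severe event is Grade 5, though that event is visible in several other outputs.

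The size is unknown beyond 0.67 percentage points per misclassified patient in Parts A and B. The conclusion rests on the wording of the current SAP and on no assumption about how often PECs worsen. It is an inexpensive improvement that brings the SAP into line with the protocol; it does not show that any reported rate is wrong.

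**What to change.** In SAP 5.3.9.2:

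- Keep the all-AE table by grade within SOC. Protocol 12.2.12 also asks for the severity of all reported AEs, so replacing it would open a new mismatch.
- Add a TEAE table by each patient's maximum on-treatment CTCAE grade within SOC, once for all causality and once for possibly related events.
- Change the overview row, or add one, to count patients with at least one TEAE of Grade 3 or higher, with Grade 5 shown separately.
- State that in these TEAE outputs a worsened PEC is counted at its worsened grade and an unchanged one is not counted, and say whether PECs enter the all-AE table.

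The cost is some SAP wording, one filter, one row and one further table from data already collected. Protocol 12.2.8 already provides for later SAP versions that could carry the change. The severe-event rate may look slightly less favourable once worsened conditions and Grade 5 events are included.
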